Following the MRS scan, subjects will be provided a standard breakfast, and then will begin ~3 days and 3 hours of fasting. During the fast, subjects will be allowed to drink water ad libitum and to perform normal ambulatory activity, excluding exercise. A subcutaneous continuous glucose monitoring system will be utilized to track glycemia during the first 72 hours of the fast. After approximately 24, 48, and 72 hours of the initiation of the fast, blood (10mL for study use and 10mL for future use if the participant provides permission) and urine will be collected, weight and vital signs measured, and adverse events recorded. At 72 hours of the fast, measurement of glial metabolism will be repeated via MRS. Subjects will then be provided breakfast (Standard American Diet, overfed by 50%) and discharged from the Inpatient Unit after an end of study evaluation (physical, blood glucose) by the Medical Investigator.

Study Procedure Descriptions

- **Acetate infusion/MRS procedure:** Glial metabolism will be measured via MRS utilizing a simultaneous intravenous infusion of ¹³C labeled acetate. An intravenous catheter will be placed in a vein of each arm, one to infuse ¹³C-acetate and the other to draw blood samples.
 - Participant alignment and baseline scans: 30 to 40 minutes prior to the start of acetate infusion, participants will be placed in the MRI scanner to conduct both preliminary alignment via MRI as well as baseline MRS scans.
 - Acetate infusion protocol: The infusate, 350 mM [1-¹³C] acetate (99% enriched; Microbiological/Pyrogen tested), will be prepared by the PBRC Pharmacy. ¹³C-acetate will be administered for the first hour of the MRS procedure, at a rate of 6 mg/kg per minute for the first 5 minutes, and 3 mg/kg per minute for the remainder.

- Blood sampling protocol: Venous blood samples (approximately 2 mL each) will be obtained about every 10 minutes, starting 20 minutes before the beginning of the acetate infusion, and will be continued throughout the infusion (~15 total draws).
- MRS protocol: During IV infusion of [1-13C] acetate, MRS spectra will be collected every 10 minutes for 120 minutes using a 3 Tesla GE SIGNA MRI scanner housed in the PBRC Biomedical Imaging Center.

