- Analysis: The blood collection will be used to measure changes in plasma acetate concentrations and % C13 enrichment of plasma acetate over time, via mass spectrometry. The MRS spectra will be used to calculate changes in cerebral 13C enrichment of glutamine, glutamate, and bicarbonate over time, which reflects glial metabolism and glial amino acid synthesis.
- Anthropometrics: Fasting body weight will be collected with participants wearing a hospital gown and underwear. Height will be collected once at screening.
- Blood collection (study use): Approximately 37.5 mL of whole blood will be drawn during each acetate infusion/MRS assessment on Days 0 and 3 (described above), and approximately 10 mL of additional whole blood will be collected on Days 0, 1, 2, and 3. The total volume of blood that will be collected during the study is approximately 115 mL (37.5 mL + 10 mL + 10 mL + 10 mL + 10 mL + 37.5 mL). Blood will be collected during the MRS assessment to measure plasma acetate concentrations and % C13 enrichment of plasma acetate via mass spectrometry. Blood will be collected on Days 0, 1, 2, and 3 of the observational study to measure metabolic hormones of interest, such as β -hydroxybutyrate, free fatty acids, insulin, leptin, glucagon, glucose, and catecholamine concentrations.
- Blood collection (future use): For participants who provide permission, whole blood will be collected for future research (10mL at screening and 10mL at Days 0, 1, 2, and 3; 50ml total). Samples collected will be stored for future use by PBRC researchers and collaborators.
- Continuous glucose monitoring: Blood glucose will be assessed using continuous glucose monitoring (CGM). Briefly, the abdominal area will be disinfected, and then trained staff from the Inpatient Unit will insert a glucose sensor under the skin in the abdominal area. The sensor has a small needle-like probe that inserts into the subcutaneous fat of the abdomen and that measures blood glucose levels without removing blood from the body. The sensor will then be attached to the recording unit, and the set-up will be secured with adhesive to the participant's body. After an initial period of equilibration with interstitial glucose, the sensor will be calibrated about every 6-12 hours by pricking the participant's finger to measure capillary blood glucose. The CGM device records blood sugar levels every 5 minutes.

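### No bedside glucose is scheduled at scanner entry or during the 150–160 minute Day 3 scan, which begins as planned CGM tracking ends (minor safety improvement)

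*Combined protocol and SAP*

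**What the plan says.** The 4-Day Observational Inpatient Stay section plans a fast of three days and three hours. It limits planned glucose tracking: "A subcutaneous continuous glucose monitoring system will be utilized to track glycemia during the first 72 hours of the fast". It then places the second scan where that tracking ends: "At 72 hours of the fast, measurement of glial metabolism will be repeated via MRS". At about 24, 48 and 72 hours a blood sample is taken, with "weight and vital signs measured, and adverse events recorded". Blood collection (study use) includes glucose among the analytes of that sample. It does not say whether the result is known before the scan.

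Under Study Procedure Descriptions, "30 to 40 minutes prior to the start of acetate infusion, participants will be placed in the MRI scanner", and spectra are then collected for 120 minutes "using a 3 Tesla GE SIGNA MRI scanner housed in the PBRC Biomedical Imaging Center". On sampling: "Venous blood samples (approximately 2 mL each) will be obtained about every 10 minutes, starting 20 minutes before the beginning of the acetate infusion", for about 15 draws. Their stated use is limited: "The blood collection will be used to measure changes in plasma acetate concentrations and % C13 enrichment of plasma acetate over time". The CGM records every 5 minutes and is calibrated by finger-stick every 6–12 hours. Those finger-sticks are not tied to the scan.

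Table 1 marks one Day 3 finger-stick glucose. The text mentions breakfast and then has the participant "discharged from the Inpatient Unit after an end of study evaluation (physical, blood glucose) by the Medical Investigator". This fixes the reading before discharge, but not before or after the meal.

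**The concern.** Risks to Subjects tells the reader that hypoglycemic symptoms are likely during the fast. The Day 3 scan comes at the longest point of that fast, with the participant lying in a scanner, and begins as planned glucose tracking stops. A catheter is in place for sampling and blood is being drawn about every 10 minutes, yet no glucose is read from it. A low value could therefore go unnoticed until symptoms appear or the scan ends. What is at stake is participant safety. No endpoint definition or planned analysis depends on this point.

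**Working it through.** **The plan's own timing**
- Fast: 3 × 24 + 3 = 75 h.
- Planned CGM tracking: 72 h. Remainder: 75 − 72 = 3 h, and 3 / 75 = 4%.
- Scanner time: set-up of 30–40 min plus 120 min of spectra = 150–160 min.
- If the participant enters at 72 h, he leaves at 72 + 2.5 = 74.5 h to 72 + 2.67 = 74.7 h. This agrees with the planned 75 h, so he is meant to remain fasted throughout the scan.
- Draws every 10 min from −20 to +120 min: 140 / 10 + 1 = 15, which matches the stated total. If sampling stopped with the one-hour infusion: 80 / 10 + 1 = 9, which does not match. Sampling for the full 120 min is therefore the likelier reading, although the text also ties sampling to the infusion.

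**Age of the last planned CGM value** (assumes staff can see the CGM and it is worn until entry; one record per 5 min)
- At entry: 0–5 min.
- At exit: shortest 150 + 0 = 150 min (2.5 h); longest 160 + 5 = 165 min (2.75 h).

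**With readings added at entry and from draws at 0, 30, 60, 90 and 120 min**
- Entry to the 0-min draw: 30–40 min; then 30 min between readings. Longest gap: 30–40 min.
- If sampling stops at 60 min, the last draw is 120 − 60 = 60 min before the end of the scan.

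**Strips**
- 1 + 5 = 6 per man, or 6 × 10 = 60 for ten men.
- If sampling stops at 60 min: 1 + 3 = 4 per man, or 4 × 10 = 40.

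**The case against.** The strongest reply is that these men are already well covered. They are aged 18–40, without diabetes and screened as healthy, and the protocol calls the fasting risk minimal. Each has a catheter in both arms, so treatment could be given at once, and sampling brings staff contact about every 10 minutes. At 72 hours there are vital signs, an adverse-event check and a blood sample that includes glucose. The scan can be halted, a physician is on call, the Medical Investigator monitors closely, breakfast follows, and nothing forbids a finger-stick for symptoms. All of this stands, and it is why the point is minor. It does not supply a scheduled reading.

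Four stronger readings are tempting, and the documents do not support them.
- *Supervision lapses at the scanner.* The protocol speaks of supervision by nursing staff in the Inpatient Unit, and the scanner is elsewhere. The phrase can equally identify which staff supervise; the CGM description uses similar wording in that sense.
- *The last bedside value could be 14.7 hours old at exit.* This is 12 + 2.67 h. It requires that staff cannot see the CGM, that no extra finger-stick is taken and that calibration is at its widest spacing. Twelve of those hours are ordinary spacing that applies throughout the fast; the scan adds only 2.5–2.7 h.
- *The planned finger-stick should move to before breakfast.* Moving it could remove the only glucose reading between refeeding and discharge. The unspecified order permits a post-meal check, which is a reasonable choice.
- *A fixed glucose level for stopping the Day 3 scan is the remedy.* No action level is stated for any part of the fast, so a rule for the scan alone would leave the preceding 72 hours without one. Aim 2 asks whether the magnitude of fasting hypoglycemia predicts glial change. A stopping level would selectively remove the most hypoglycemic men from the MRS data.

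The study-design figure is not available in the text reviewed and may show further Day 3 timing.

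**Conclusion.** The gap is real but small. In about 3 of 75 hours, for up to ten men, no bedside glucose is scheduled at scanner entry or during a scan of 150–160 minutes. The last planned CGM value is about 2.5–2.75 hours old at exit, assuming the CGM is visible to staff and worn until entry; the documents state neither. That figure measures the age of a reading, not a risk of harm. The documents give no basis for calling these hours more dangerous than those before them. The point is worth acting on because the protocol itself expects symptoms and the blood needed is already being drawn.

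**What to change.** On Day 3:
1. Take a bedside glucose just before scanner entry, by finger-stick or a drop from the 72-hour draw.
2. Read glucose on a meter kept outside the magnet room from a few of the existing serial draws, for example every 30 minutes while sampling continues.
3. Report each value at once to the responsible clinician, who decides on treatment or stopping the scan.
4. Keep the end-of-study glucose as the discharge check. If a pre-breakfast reading is wanted, add one.

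If the team sets a glucose action level, it should apply to the whole fast. Any scan stopped for low glucose should be reported as non-random loss, with its bearing on Aim 2 stated.

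The cost is about 4–6 strips per man (40–60 for ten men), one more per man if a separate pre-breakfast reading is added, and a little staff handling. No extra venous draw is needed. A Day 3 scan may occasionally be lost. Enrolling ten to obtain six complete leaves 10 − 6 = 4 men for losses from all causes, but that margin replaces numbers only and does not undo the selective loss.

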Our eligibility criteria for the study is limited to males in an effort to reduce variability within our small sample size due to the known gender differences in the physiological response to hypoglycemia both acutely (22, 23), as well as during a 72-hr fast (24). Previous studies have demonstrated a reduced release of counterregulatory hormones (e.g. epinephrine and glucagon) in response to hypoglycemia in women. Given that this is a pilot study with a limited number of participants to be studied, we have chosen to minimize the potential variability in our outcome measures caused by these gender differences, by limiting our enrollment to males. This will allow us to minimize our participant numbers.

Number of Subjects

Up to ten subjects will be enrolled in this study.

Recruitment Methods

Standard recruitment methods (email, print, social media advertisements, etc.) will be used to identify potential participants. As this is a study requiring consecutive overnight stays at the Inpatient Unit at Pennington Biomedical, the PI may submit a privacy board request identifying potentially eligible participants who have previously completed extended-stay studies at Pennington Biomedical and have consented to future contact.

Study Timelines

A participant's duration of study participation will be approximately 4 days.

The estimated duration to enroll all study subjects is anticipated to be nine months.

The estimated duration to complete the study (primary analyses) is 1 year (April 2016)

Study Endpoints

Primary endpoints:

- Percent ^{13}C enrichment of cerebral glutamine, glutamate, and bicarbonate, as measured by magnetic resonance spectroscopy (MRS)
- Glial acetate oxidation rate and astroglial TCA cycle rate ascertained through mathematical modeling of MRS data

Secondary endpoints:

- Change in glucose levels
- Change in leptin levels

Procedures Involved

The study design and schedule of assessments are depicted in **Figure 1** and **Table 1**.

Measurement	Screening Visit	Observational Study Visit			
		Day 0	Day 1	Day 2	Day 3
Height	X				
Weight	X	X	X	X	X
Medical History	X				
Physical exam	X				X
Blood collection		X	X	X	X
Blood collection for future use**	X	X	X	X	X
Urine collection	X	X	X	X	X
Blood glucose*	X				X
ECG	X				
CGM		X	X	X	X
Vital signs	X	X	X	X	X
¹³ C - MRS†		X			X
DXA		X			
Adverse events			X	X	X

*via finger-stick.
 **Optional
 †IV procedure and serial blood collection
 CGM: Continuous glucose monitoring

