- DXA: Dual X-ray absorptiometry (DXA) scans will be performed using a General Electric Lunar iDXA whole-body scanner (General Electric, Milwaukee, WI) during the first day of the Inpatient stay. The protocol requires that subjects lie on a table wearing a hospital gown and no metal containing objects, while the scanner emits low energy X-rays and a detector passes along the body. The scan takes approximately 10 to 15 minutes and the radiation dose is less than 1 mrem, equal to about 12 hours of background radiation. In our hands at PBRC, the standard deviations for DXA measurements are 320g (CVs of 0.6%) and 300g (CVs of 1.1%) for FFM and FM, respectively.

- Ketonuria: Participants will collect a small urine sample in a provided collection cup and ketonuria will be assessed using a Ketostix® (mg/dL).
- Vital Signs: Vital signs will be collected according to PBRC standard operating procedures. Seated vital signs (blood pressure and heart rate) will be measured after a 5 minute rest.

Data and Specimen Banking

Biospecimens banked for future use will be stored indefinitely at Pennington Biomedical in the Clinical Chemistry and [name] Laboratories. Data will be stored with the participant's de-identified ID number. Specimens will be labeled with the participant's de-identified ID number and date of collection. Data and specimens are accessible by the PI, his staff and designated Clinical Chemistry staff in buildings with restricted access. Requests for release of data and/or specimens will be considered by the PI or a study investigator. Upon agreement to release data and/or specimens, material and/or data transfer agreements will be drafted and approved by respective parties prior to the release of any material.

Power analysis

The primary outcomes of this study are ¹³C enrichment of brain glutamine and glutamate, measured by MRS. An a priori power analysis was performed by the Biostatistics and Epidemiology Core using means, standard deviations, and effect sizes previously reported in a similar study (20). This analysis estimated that a sample size of 6 would provide adequate statistical power for our primary outcome variables (Table 2). This protocol allows for enrollment of ten subjects to account for withdrawals and allow for complete data on six subjects.

Mean Diff	SD	Power	N
4.0	2.3	0.845	8
4.5	2.3	0.860	7
5.0	2.3	0.849	6
5.5	2.3	0.804	5
6.0	2.3	0.863	5

Data and Specimen Management

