Study data collected and entered into the Pennington Biomedical Database is handled only by individuals with appropriate HIPAA compliance and Good Clinical Practice training. Participant charts and hard copy data are stored in locked offices with restricted access. Electronic data has exclusive restricted access granted by the Research Computing Group and/or the PI. For quality control, data and charts will be audited for completeness and accuracy (when possible).

Study data and specimens will be stored indefinitely at Pennington Biomedical in the Clinical Chemistry and [name] Laboratories. Data will be stored with the participant's de-identified ID number. Specimens will be labeled with the participant's de-identified ID number and date of collection. Data and specimens are accessible by the PI, his staff and designated Clinical Chemistry staff in buildings with restricted access.

Data analyses will be conducted as follows:

Acetate infusion/MRS procedure: Using the time courses of ¹³C enrichment of glutamate, glutamine and bicarbonate (from MRS spectra), as well as the time courses of plasma acetate ¹³C enrichments (from mass spectroscopy on plasma) we will

mathematically model several parameters of cerebral metabolism, such as brain acetate concentrations ($[\text{acetate}]_{\text{BR}}$), Glial acetate oxidation rate (V_{gac}), and astroglial TCA cycle rate ($V_{\text{TCA}}A$). Each subject will participate in two MRS scans, one immediately prior to, and one immediately following a 72-h fast. Repeated measures ANOVA will be used to compare the mean values of percent enrichment of cerebral glutamine, glutamate, and bicarbonate over time, as well as $[\text{acetate}]_{\text{BR}}$, V_{gac} , and $V_{\text{TCA}}A$ measured before and after the 72-h fast, i.e., differences between first and second MRS assessments. P-values < 0.05 will be considered significance.

Serum hormone and metabolite measurements: Mean values of serum hormone and metabolites (including glucose) measured at each time point will be compared via repeated measures ANOVA. P-values < 0.05 will be considered significance.

Additional analysis: Correlation analysis will also be used to determine if changes in the parameters measured via our acetate infusion/MRS procedure are related to changes in our serum hormone and metabolite measurements.

Provisions to Monitor the Data to Ensure the Safety of Subjects

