 - *Confinement*: During the MR scan, the participant will be lying down on a table inside of a metal tube. The metal tube is a confined place. This might produce a feeling of claustrophobia, which can be distressing. A participant who has experienced claustrophobia in the past might become too distressed to complete the scan. In this case, the scan will be halted.
 - *Noise*: The MRI machine creates a loud, rhythmic noise that sounds like grinding or churning. This can be distressing to those who are sensitive to loud noises. The participant will be provided with earplugs to reduce the noise. But, if the participant finds the machine noises distressing, the MR technician can halt the scan.
 - *Peripheral nerve stimulation*: During the MR scan, the magnetic field around the body goes through rapid changes. These changes are all within safety limits set by the Food and Drug Administration. But, some people experience twitching in the nerves of their arms or legs as a result

of these magnetic field changes. This twitching is generally not painful, and it stops at the end of the MR scan. But the feeling of inadvertent muscle twitching may make individuals feel disoriented or uncomfortable. Any participant who experiences this and wishes to stop the scan as a result will be allowed to do so.

- Continuous Glucose Monitoring (CGM): Because CGM involves the placement of an implantable device below the skin, there is the possibility of discomfort, pain, and bruising at the site where the device is inserted. There is also a small risk of bleeding and a very small risk of infection at the site of the blood draw. Aseptic (sterile) technique and trained personnel minimize these risks. Finally, the adhesive may cause redness or irritation of the skin.
- Prolonged fasting (72 hours): The risks associated with prolonged fasting are minimal in healthy adults, and is routinely used in clinical research studies (e.g. 22, 23), as well as for clinical diagnoses of insulinoma (e.g. 23, 24, 25). Participants are likely to experience symptoms of hypoglycemia including cold sweats, palpitations, shakes, unsteadiness, drowsiness. The participants will be continually supervised by the nursing staff in the Inpatient Unit to ensure safety, and any adverse events will be recorded.

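### The serum analysis gives no rule for men who stop the fast early; classical repeated measures ANOVA would drop all their samples, and a mixed model would keep them.

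*Combined protocol and SAP*

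**What the plan says.** The serum paragraph of the data-analysis text (under Data and Specimen Management) says that means are "measured at each time point will be compared via repeated measures ANOVA" and that "P-values < 0.05 will be considered significance". It names no estimation method, covariance structure, analysis set or missing-data rule. Blood for these assays is drawn on Day 0 and at about 24, 48 and 72 h of the fast, so each completer has four values.

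Study Endpoints lists two secondary endpoints, "Change in glucose levels" and "Change in leptin levels". Neither has a stated time point, and glucose is not tied to serum or to continuous glucose monitoring (CGM).

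Three other sections bear on incomplete records:

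- Power analysis: "This protocol allows for enrollment of ten subjects to account for withdrawals and allow for complete data on six subjects".
- Withdrawal of Subjects: a man who does not keep to the fast may be withdrawn. Nothing is said about samples he has already given.
- Risks to Subjects, on prolonged fasting: "Participants are likely to experience symptoms of hypoglycemia".

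**The concern.** A man who stops after the 48 h draw has valid values at 0, 24 and 48 h. Classical repeated measures ANOVA works on full rows, so with no other rule those three values leave the analysis because the fourth is missing. In a study of at most ten men that is a material loss.

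The loss may also be selective. One ground for withdrawal is failing to keep to the fast, and hypoglycemic symptoms are expected during it. Men whose glucose falls further could therefore be the ones who stop, and an analysis of completers would then show too small a fall. The two secondary endpoints are at stake.

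**Working it through.** **The plan's own figure.** The only power statement is 0.849 at N = 6 for a mean difference of 5.0 with SD 2.3. It reproduces as a two-sided paired t-test at 0.05 with SD of the difference 2.3 × √2 = 3.25. It concerns the MRS outcomes. The documents give no serum mean, SD, power or dropout rate, so every serum figure in mg/dL below rests on assumed inputs.

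**Samples lost if four of ten stop and only full rows are used (counts only)**

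| All four stop after | Collected | Unused |
|---|---|---|
| Day 0 draw | 6×4 + 4×1 = 28 | 4 (14%) |
| 24 h draw | 6×4 + 4×2 = 32 | 8 (25%) |
| 48 h draw | 6×4 + 4×3 = 36 | 12 (33%) |

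Four is the most that still leaves six completers. For at least one early stop among ten, the chance is 1 − (1 − d)^10: 65%, 89% and 99% at assumed dropout d of 10%, 20% and 40%.

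**Precision when stopping is random.** Assumed glucose means are 90/75/68/65 mg/dL, SDs 6/7/8/8 and AR(1) correlation 0.7. Four men lack only the 72 h draw. The variance of a within-man change is s0² + st² − 2ρ·s0·st.

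- 24 h: 36 + 49 − 2(0.7)(42) = 26.2, SD 5.12. Completers 5.12/√6 = 2.1; all ten 5.12/√10 = 1.6.
- 48 h: 36 + 64 − 2(0.49)(48) = 52.96, SD 7.28. Completers 7.28/√6 = 3.0; all ten 7.28/√10 = 2.3.
- 72 h, completers: 36 + 64 − 2(0.343)(48) = 67.07, SD 8.19, and 8.19/√6 = 3.3.
- 72 h, likelihood with known covariance: the six completers supply the 72 h value given the 48 h value, with variance 64(1 − 0.49)/6 = 5.44. All ten supply the rest, with variance (0.49×64 + 36 − 2×0.7×0.49×48)/10 = 3.44. The SD is √8.88 = 3.0.

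Simulated fits of parsimonious mixed models gave 3.0 to 3.1 at 72 h against 3.4 for completers. An unstructured covariance, simulated with the four lowest men at 48 h stopping, raised the 72 h SD to 4.7. The gain is therefore at 24 and 48 h, and the covariance should be simple.

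**Bias when the four lowest men at 48 h stop.** The six highest of ten normal values average 3.572/6 = 0.595 SD above the mean.

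- 48 h: 0.595 × (8 − 0.49×6) = 3.0, so completers show −19.0 against a true −22.0.
- 72 h: 0.595 × (0.7×8 − 0.49×6) = 1.6, so completers show −23.4 against −25.0.
- The likelihood estimate with known covariance returns −22.0 and −25.0.

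**How far this depends on the mechanism**

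- Random stopping: no bias by either method.
- Only the two lowest at 48 h stop: the eight highest average 2.540/8 = 0.3175 SD above the mean, and 0.3175 × 2.66 = 0.8. Completers show −24.2 at 72 h, about 3% too small.
- The men lowest at 72 h are the four missing: in 800 simulated trials completers gave −21.3 and parsimonious mixed models −21.8 to −22.3, against −25.0. The remaining bias is 2.7 to 3.2 of 3.7, roughly three quarters or more.
- Compound symmetry (assumed SD 8): if stopping follows observed glucose, completers have about no bias in the 0–72 h change. If it follows the unobserved value, the mixed model can be the worse of the two (+1.6 against +1.1 at 40% dropout, correlation 0.3).

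**The case against.** The plan never says complete-case or completers only. A reader might infer that it prescribes discarding partial records, but that is read into the name of the method. A repeated measures analysis can be fitted as a mixed model that keeps them. This stands, and the point is limited to what the classical form does when no other rule is given.

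A reader might also infer an expected 40% dropout. Ten is an enrolment ceiling, and the sentence about complete data on six men sits in the power analysis for the MRS outcomes. This too stands: four incomplete men is what the ceiling allows, not a forecast.

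The link between stopping and glucose is assumed. The risk section expects symptoms in participants generally and does not say that those with the deepest fall will stop. Leaving campus is another stated ground for withdrawal, and a scan may be halted for claustrophobia or noise; neither need depend on glucose. The illustration with the four lowest men stopping is a severe case. Even there the 72 h bias (1.6 mg/dL) is about half the SD of the estimate (3.3).

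CGM records glucose every 5 minutes, so an early stopper's fall is partly captured. That is true, but no analysis of the CGM record is described, and it gives nothing for leptin.

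Finally, this is a pilot and these are secondary endpoints. That limits the weight of the point. It does not justify leaving collected samples unused when the remedy needs no new data.

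**Conclusion.** The point holds as a gap with a cheap remedy. As named, and with no rule for early stopping, the serum ANOVA would in its classical form lose up to 12 of 36 collected samples if four men stopped after the 48 h draw. The precision cost arises even with random stopping. Under the assumed means, SDs and AR(1) correlation of 0.7, the SD of the change is 2.1 against 1.6 mg/dL at 24 h and 3.0 against 2.3 at 48 h, with little to gain at 72 h.

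It would go too far to say that the glucose and leptin endpoints are biased toward men who tolerated the fast. Bias in glucose is plausible from the withdrawal and risk sections, but it ranges from none to several mg/dL depending on why men stop, and the documents do not settle that. No leptin figure can be given.

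Nor does the point repair Aim 2. A man who stops early has no 72 h scan, so he has no MRS change to correlate, whichever serum model is used.

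**What to change.** Replace the serum ANOVA sentence with a prespecified likelihood-based linear mixed model: time as a factor, a parsimonious covariance such as AR(1) or compound symmetry, and Kenward-Roger degrees of freedom. Use the Day 0 sample and every later sample drawn before the fast is broken. Name the time point that defines each secondary endpoint.

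Add a short table of baseline and last-available glucose and leptin, with reasons for stopping, for non-completers beside completers. It makes any narrowing of range in the Aim 2 data visible.

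State two limits. The model does not remove bias at 72 h if stopping depends on values not observed, so add a simple sensitivity analysis; the CGM record up to stopping can inform it for glucose. The model also adds no pairs to the Aim 2 correlations.

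The cost is a few sentences of SAP text and a standard model fit, with no extra visits or samples. The small downside is that a covariance structure must be chosen in advance.
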